- h Women of childbearing potential, only. Urine test on Day -1 for Day 1 prior to infusion; serum test during Screening and on Day 29. Central lab should assess serum sample collected at screening and on Day 29, but the local lab can assess the urine test on Day -1/Day 1 prior to the infusion.
- Duplicate samples for IgG should not be drawn if sample was already taken with safety labs collection.
- Duration of infusion is based on dosing instructions (details provided in the pharmacy manual). Patients will be required to drink 2 glasses of liquid in the morning before the start of infusion. Just before infusion, patients will be provided the opportunity to urinate. Patients receiving M254 or IVIg can be discharged 4 hours post-infusion.
- If infusion duration is <20 minutes, end of infusion activities may be scheduled as logistically feasible with the PK sample drawn from 1 minute before the end of infusion to 2 minutes after the end of infusion. For infusion durations ≥20 minutes, activities should occur in the order of the table (top to bottom) unless a footnote indicates otherwise.
- All systemic infusion reactions and associated AEs will be graded using Common Terminology Criteria for Adverse Events (CTCAE).
- Patients with ITP may admit to the unit the morning of Day 1so any procedure specified on Day -1 can occur on Day 1, but all results must be back before infusion begins. Likewise, any pre-infusion assessment specified on Day 1 can occur on Day -1 and does not need to be duplicated.
- Study staff should follow-up with the patient approximately 12 hours post-discharge for safety via phone call.
- O Discharge from study after final study period unless further follow-up of open AEs is deemed necessary by the Investigator.
- M254 or IVIg infusion will occur on this day if patient's platelet count meets criteria, and then the Schedule of Activities should be followed starting at Day 1. For Period 2, Day 1, any assessments completed on the same date for Period 1 follow-up do not need to be duplicated.
- q Blood sample for PK is required during the M254 treatment period only. It is NOT needed for the IVIg treatment period.

Compound: M254

Protocol: MOM-M254-001

- r ITP-BAT to be completed separately at Day 1 and 29 of each period (M254- and IVIg-treatment). Only 1 ITP-BAT assessment is needed if Day 29 of the first period is the same as Day 1 of the second period.

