- Women of childbearing potential, only. Urine test on Day -1; serum test during Screening and on Day 29. Central lab should assess serum sample collected at screening and on final follow-up, but the local lab can assess the urine test on Day -1/Day 1 prior to the infusion.
- b Duplicate samples for IgG should not be drawn if sample was already taken with safety labs collection.
- Duration of infusion is based on dosing instructions (details provided in the pharmacy manual). Patients will be required to drink 2 glasses of liquid in the morning before the start of infusion. Just before infusion, patients will be provided the opportunity to urinate. Patients receiving M254 can be discharged 4 hours post-infusion.
- m If infusion duration is <20 minutes, end of infusion activities may be scheduled as logistically feasible with the PK sample drawn from 1 minute before the end of infusion to 2 minutes after the end of infusion. For infusion durations ≥20 minutes, activities should occur in the order of the table (top to bottom).
- n All systemic infusion reactions and associated AEs will be graded using Common Terminology Criteria for Adverse Events (CTCAE).
- Patients with ITP may be admitted to the unit the morning of Day 1 instead of Day -1. Any procedure specified on Day -1 can occur on Day 1, but all results must be back before infusion begins. Likewise, any pre-infusion assessment specified on Day 1 can occur on Day -1 and does not need to be duplicated.
- p Study staff should follow-up with the patient approximately 12 hours post-discharge for safety via phone call.
- Discharge from study after final study period unless further follow-up of open AEs is deemed necessary by the Investigator.
- M254 infusion will occur on this day if patient's platelet count meets criteria, and then the Schedule of Activities should be followed starting from whichever infusion the patient is scheduled for in Part D, ie, 2nd, 3rd, or 4th. Any assessments completed on the same date from the prior infusion period follow-up do not need to be duplicated.

Compound: M254 Momenta Pharmaceuticals, Inc.

Protocol: MOM-M254-001

- s ITP-BAT to be completed at Day 1 prior to infusion.
- t ECG and vital sign assessments required at the end of the infusion may be initiated 15 minutes prior to the end of infusion
- u These should be conducted as abbreviated physical exams

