- PK sample is required prior to the start of infusion (on the day of the infusion).
- W Skip indicates that no assessments occur on these days.
- x ADA samples are collected at each pre-infusion and the final follow-up visit. Please refer to the lab manual for specific instructions.

Compound: M254 Protocol: MOM-M254-001

Protocol Date and Version:8 Global 28 April 2020

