## 4.1.4 Part D (USA sites included)

Part D is a repeated, fixed-dose, open-label study of M254. Any patients who participate in Parts B or C are allowed to participate in Part D if they meet inclusion criteria during screening for Part D. Part D may have up to 2 dose levels with up to approximately 15 to 34 ITP patients in total. The initial dose level for Part D will be less than or equal to the maximum tolerated dose, and it will be selected based on review of Part B data and available data from Part C. Following completion of Part C, the dose for new patients in Part D may be revised (the dose level will not be modified for patients who have already received at least 1 dose). Patients who have participated in Part B or C may be allowed to participate in Part D, prior to completion of randomization in Part C. New patients not in Part B or C may participate in Part D following complete randomization in Part C. The dose levels of M254 for Part D will be determined after analysis of available data from Part A, Part B, and Part C.

Following screening to confirm eligibility to participate (including rescreening patients who participated in Part B or C), M254 naïve patients will receive 4 doses of M254, and patients from Part B or C will receive 3 doses of M254 every 14 days. Patients in Part C may roll over into Part D by including any data after the last dose of IVIg or M254 in Part C for assessment of screening in Part D as long as those data are within the screening window specified. Please refer to Section 4.3.1 and Figure 1-5 for dosing details.

If the patient's platelet count has not returned to  $\leq 100 \times 10^9 / L$ , their platelet count will be monitored weekly until platelets return to  $\leq 100 \times 10^9 / L$ . If these conditions are not met, M254 will not be administered further. Patients will be followed for safety assessments and platelet counts up to at least 28 days post their last dose of M254. Safety will be reviewed by the SRC quarterly (or more often as required).

Blood for safety labs, PK, and PD will be collected as defined in the Schedule of Activities (Table 1-4).

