## 8.3.7 Pregnancy Screen

A serum pregnancy test will be conducted at screening and on Day 29 for all female participants of childbearing potential. A urine pregnancy test will be conducted on Day -1.

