# **Pregnancy Testing:**

- Women of childbearing potential should only be included after a confirmed menstrual period and a negative highly sensitive serum pregnancy test.
- Additional pregnancy testing is required during Day 1 of the treatment period and at follow-up visit, corresponding to protocol-defined time frame in Section 5.1 after the last dose of study intervention and as required locally.
- Pregnancy testing will be performed whenever a menstrual cycle is missed or when pregnancy is otherwise suspected.

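### Part D puts the last serum pregnancy test both on Day 29, a dosing day, and at final follow-up, and its grid schedules no test before the repeat infusions

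*Protocol*

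**What the plan says.** **Date of the later serum test.** The Part D pregnancy footnote (Protocol Section 1.2, Table 1-4 and Table D2) gives two dates in consecutive sentences: "serum test during Screening and on Day 29. Central lab should assess serum sample collected at screening and on final follow-up". Section 8.3.7, which is not specific to a study part, says "A serum pregnancy test will be conducted at screening and on Day 29 for all female participants of childbearing potential". Table 1-4 marks the test at screening, Day -1 and follow-up only. Section 8.1.3 sets the Part D follow-up visit at Day 71 (M254-naive) or Day 57 (from Part B or C). Appendix 4 (Section 10.4) says "Additional pregnancy testing is required during Day 1 of the treatment period and at follow-up visit", and that bullet goes on to allow for local requirements. In the Part C footnote the corresponding sentence reads "Central lab should assess serum sample collected at screening and on Day 29", and Day 29 is the follow-up visit there.

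**Tests before dosing.** Section 4.1.4 gives M254-naive patients four doses, while "patients from Part B or C will receive 3 doses of M254 every 14 days". Table D2, which governs the infusion days, has no pregnancy row. The footnote ties the urine test to Day -1 or Day 1. Inclusion criterion 9 and exclusion criterion 3 (Sections 5.2.1 and 5.2.2) likewise refer to screening and to baseline or Day 1. For repeat infusions, footnote r says: "M254 infusion will occur on this day if patient's platelet count meets criteria".

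SAP Appendix 2 reproduces the same tables and footnote.

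**The concern.** The date conflict can be acted on in two ways. A site that follows the grid tests at the end of the study. A site that follows the Day 29 wording, which Section 8.3.7 supports, could draw serum on a dosing day and omit the end-of-study test. For an M254-naive patient the last serum test would then come before the last dose.

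The second matter concerns exposure. Appendix 4 requires a participant who becomes pregnant to stop study intervention or be withdrawn. That rule works only if the pregnancy is found. Part D is the only repeat-dose part of a first-in-human study, and its schedule has no routine check between the first dose and the later ones.

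**Working it through.** No sample size, power or error rate is involved. The check compares the schedule entries and uses day arithmetic.

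**Inputs**
- Infusion days (Table D2): 1, 15, 29, 43 for M254-naive patients; 1, 15, 29 for patients from Part B or C.
- Final follow-up (Table 1-4, Section 8.1.3): Day 71 or Day 57.
- Largest Part D enrolment (Section 4.1.4): 34.
- Contraceptive failure rate (Appendix 4): below 1% per year with consistent and correct use, taken here as 1%.

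**1. Distance between the two dates**
- M254-naive: 71 − 29 = 42 days.
- From Part B or C: 57 − 29 = 28 days.

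If Day 29 alone were followed, a naive patient's last serum test would fall 43 − 29 = 14 days before the final dose.

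**2. Infusions with no scheduled test**

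| Reading | M254-naive | From Part B or C |
|---|---|---|
| Grid (screening, Day -1 or 1, final follow-up) | Days 15, 29, 43: 3 of 4 | Days 15, 29: 2 of 3 |
| Grid plus a Day 29 serum test, result back before dosing | Days 15, 43: 2 of 4 | Day 15: 1 of 3 |

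The second row is optimistic. The footnote sends the scheduled serum samples to the central laboratory, and nothing specific to a Day 29 serum sample says that its result must precede that day's infusion.

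**3. Period in which an added test could prevent a dose (nominal schedule)**
- M254-naive: 43 − 1 = 42 days.
- From Part B or C: 29 − 1 = 28 days.

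**4. Expected pregnancies in that period**

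Expected number = women of childbearing potential × annual rate × days / 365. The documents do not give the number of women of childbearing potential, so all 34 patients are counted.
- All M254-naive: 34 × 0.01 × 42/365 = 0.039.
- All from Part B or C: 34 × 0.01 × 28/365 = 0.026.

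**5. Added tests**
- All M254-naive: 34 × 3 = 102.
- All from Part B or C: 34 × 2 = 68.

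**The case against.** **The date conflict is clerical and the documents resolve it.** The grid, the footnote's second sentence, Section 8.1.3 and Appendix 4 all point to final follow-up. A site that followed both sentences would only add a harmless test. This largely stands and is a reason for the low severity. The conflict still needs correcting, because Section 8.3.7 independently supports the wrong day.

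**Testing at baseline only is a consistent design choice.** This also stands. A reader might infer that the protocol meant to require a test before every infusion and left it out, or that it contradicts itself on this. The documents do not support that: inclusion 9, exclusion 3, Section 8.3.7, Appendix 4 and the footnote all tie the pre-dose test to baseline or Day 1. The request for repeat tests is a recommendation, not the correction of a broken requirement.

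**The Day -1 procedures may recur before each dose.** Footnote o is printed against the repeat dosing days and says "Any procedure specified on Day -1 can occur on Day 1, but all results must be back before infusion begins". Anti-drug antibody sampling also lacks a row in Table D2, yet footnote x says "ADA samples are collected at each pre-infusion and the final follow-up visit". On this reading no infusion would be untested. But footnote o says when a Day -1 procedure may be done, not that the pregnancy test recurs. The pregnancy footnote lacks the word each, and Table D2 repeats at Hour 0 only 8 of the 15 procedures that Table 1-4 marks on Day -1, without the pregnancy test.

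**Other safeguards exist.** Contraception is required, Appendix 4 calls for a test on a missed cycle or suspected pregnancy, and local rules may add tests. These stand, and the estimate gives the event-driven and local tests no credit. It also counts every conception in the period as preventable, although one shortly before a dose would not yet be detectable.

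**Conclusion.** The point holds at minor severity. The Part D footnote and Section 8.3.7 name the wrong day for the last serum test: Day 29 is a dosing day in Part D, and the rest of the protocol supports Day 71 or Day 57. The explanation that the wording was carried over from Parts B and C is an inference, though a natural one. On the schedule grid, 3 of 4 or 2 of 3 infusions have no scheduled pregnancy test, and only event-driven or locally required testing applies between Day 1 and final follow-up.

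The expected number of pregnancies is at most about 0.04, on three assumptions: all 34 patients are M254-naive women of childbearing potential, the failure rate is 1% per year, and doses are given on the nominal days. Weekly platelet monitoring can delay a dose and lengthen the period. A reader might infer a larger figure from the Appendix 4 note that typical-use failure rates may differ, but the documents give no such rate, so none is used. Nor do they describe an embryo-fetal hazard of M254; the Investigator's Brochure is not among them. No endpoint, analysis set or estimate is affected. The SAP tables only copy the protocol schedule and are not a second defect.

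**What to change.** **Date.** In the Part D footnote and in Section 8.3.7, state that in Part D the last serum test is at final follow-up (Day 71 for M254-naive patients, Day 57 for patients from Part B or C), not on Day 29.

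**Repeat infusions.** Add a row to Table D2: urine pregnancy test, women of childbearing potential, negative result before infusion. Mark it at Hour 0 of Days 15, 29 and 43 (M254-naive) or Days 15 and 29 (from Part B or C). Align the Part D footnote, Section 8.3.7, the Appendix 4 testing bullet and the SAP Appendix 2 copy.

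**Cost.** Wording changes in the protocol and the SAP copy, and at most 102 urine tests. Table D2 already collects urine at Hour 0 of every infusion day for urinalysis, and the footnote already lets the local laboratory read the urine test, so no new sample or visit is needed.

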### 2 INTRODUCTION

# 2.1 Study Rationale

Intravenous immunoglobulin (IVIg) is a therapeutic blood product prepared from the pooled plasma of 3,000 to 60,000 healthy donors per batch [1, 3, 7]. It is a complex heterogeneous mixture of immunoglobulin (Ig) G subclasses and low amounts of immunoglobulin A (IgA), immunoglobulin M (IgM), and other plasma proteins [15]. Intravenous immunoglobulin contains a variety of antibodies present in human serum, and the large number of donors ensures diversity in the Ig repertoire that far exceeds that of an individual donor [13].

Intravenous immunoglobulin has been used for the treatment of a variety of acute and chronic autoimmune and systemic inflammatory diseases for decades [1, 3, 15, 13]. At the current maximal dosing regimens, only partial and transient responses are obtained in many clinical instances [3, 15]. In addition, the long infusion times (4 to 6 hours) associated with the high volume of IVIg treatment consume significant resources at infusion centers [6] and negatively affect patient-reported outcomes, such as convenience and quality of life [9]. M254 is expected to be many fold more potent compared to commercially available IVIg based on preclinical pharmacological experiments. This may lead to reduced infusion time for patients compared to commercially available IVIg. Hypersialylation may increase IVIg-related anti-inflammatory and immune-modulating activities.

Alterations in endogenous IgG sialylation have been reported to be associated with treatment response in inflammatory/autoimmune diseases [1, 4]. M254 is a hypersialylated immunoglobulin engineered from commercially available IVIg ( ). M254 has demonstrated increased anti-inflammatory activity over IVIg in several arimal models, including collagen antibody-induced arthritis and pemphigoid skin blistering [23], K/BxN – sera-induced arthritis model and an immune thrombocytopenia (ITP) mouse model [23]. These findings support the clinical development of M254 for ITP and (antibody-induced) inflammatory diseases.

Intravenous immunoglobulin is an approved therapy for the treatment of ITP with prompt increases in platelet counts as early as a day after treatment with peak platelet response occurring within 2 to 7 days. This known treatment effect with easily measurable pharmacodynamics (PD) endpoint of increasing platelet count makes ITP patients a suitable population for investigation of M254. The present 4-part (each part will be initiated sequentially), first in-human study will be conducted first in healthy subjects and subsequently in ITP patients to evaluate the safety, tolerability, pharmacokinetics (PK), and PD platelet response of M254 administered as single followed by multiple intravenous (IV) doses.

The study will be executed in 4 distinct parts. Part A (Netherlands only) will assess safety, tolerability, and PK of M254 after administration of a single ascending dose in healthy volunteers. Part B will assess safety, tolerability, and PK of M254 after administration of a single ascending dose followed by 1000 mg/kg IVIg administration in ITP patients. Part C will be a 2 arm, crossover design comparing the PD platelet response of M254 with IVIg in

Compound: M254 Protocol: MOM-M254-001

Protocol Date and Version:8 Global 28 April 2020

patients with ITP. Part C will have 2 cohorts at M254 dose levels to be selected from Part A and Part B. Part D will be a repeat dose study of M254 for the evaluation of safety, tolerability, PK, and PD platelet response in patients with ITP.

## 2.2 Background

## 2.2.1 Disease Background

Primary ITP is an acquired autoimmune disorder affecting both children and adults, characterized by a platelet count below  $100 \times 10^9$ /L. The incidence of ITP in adults is around 4 per 100,000 people per year. Clinical manifestations include petechiae, purpura, bruising, and overt bleeding. Previously, 'acute ITP' was used to describe a self-limited form of disease and 'chronic ITP' thrombocytopenia described the disease if it lasted for more than 6 months. In 2009, new terminology for ITP was agreed upon based on the duration of the disease. The new terms for ITP are: 'newly diagnosed' (from diagnosis until 3 months), 'persistent ITP' (3 to 12 months) and 'chronic ITP' (ITP lasting for more than 12 months) [21, 20].

Bleeding is highly variable and there is great heterogeneity in primary ITP. Bleeding is most commonly mucocutaneous, involving gum bleeding, blood blisters in the mouth and menorrhagia. Major bleeding is not common if the platelet count is above  $30 \times 10^9$ /L. The most serious form of bleeding, intracranial hemorrhage, is rare and is most often seen in older patients who have additional comorbidities and in patients who fail to respond to therapy [20].

Diagnosis of ITP is mainly based on exclusion, when the history, physical examination, complete blood count (CBC) and examination of peripheral blood smear do not suggest other etiology for the thrombocytopenia. The low peripheral blood platelet count is caused by premature platelet destruction by self-reacting antibodies in addition to an impairment of platelet production. Autoantibodies reacting with glycoprotein (GP) IIb/IIIa may affect platelet aggregation; these are the most common autoantibodies seen in primary ITP [17].

The disease is heterogeneous in its pathophysiology, clinical features, and responses to treatment. To date, most of the treatments used have been immune-modulating drugs. Initial first-line treatment has remained unchanged for decades and comprises corticosteroids, IVIg, and less commonly anti-D in countries where the anti-D is available [18]. There have been several trials of IVIg in ITP since its first use in the mid-1980s. Intravenous immunoglobulins are sterile, purified IgG products manufactured from pooled human plasma and typically contain more than 95% unmodified IgG, which has intact fragment crystallizable (Fc)-dependent effector functions and only trace amounts of IgA or IgM. The recommended dose for commercially available approved IVIg is 1 g/kg (10 mL/kg) for 2 consecutive days. The response rate in ITP is similar to that of corticosteroids but the time to response is shorter, with a response normally seen within 24 hours although most are transient rarely exceeding 3 to 4 weeks. Toxicities include headache, renal impairment and thrombosis.

Compound: M254 Protocol: MOM-M254-001

Protocol Date and Version:8 Global 28 April 2020

## 2.2.2 Background of Investigational Product, M254

M254 is a novel hypersialylated IgG therapeutic candidate derived from commercially available IVIg, with potentially greater potency when compared to IVIg. In M254, the IgG fraction containing sialic acids has been increased. The design of M254 is based on scientific evidence illustrating the relevance of glycosylation on immunoglobulin function. In particular, it has been shown that the anti-inflammatory activity of IVIg is dependent on Fc-sialylation [18, 5].

To generate M254, IVIg is exposed to a sequential enzymatic reaction For IVIg, the sum of the all the nonsialylated glycans is >80% and the sum of all sialylated glycans is <20% [11]. For M254, the

A detailed description of the chemistry, pharmacology, efficacy, and safety of M254 is provided in the Investigator's Brochure [11].

## 2.2.3 Background of Study Product, WVIg

IVIg is commercially available. It is usually prepared from pooled plasma from not fewer than 1,000 donors. It has a distribution of IgG subclasses closely proportional to that in native human plasma. Adequate doses of this medicinal product may restore abnormally low IgG levels to the normal range.

The mechanism of action in disease indications other than replacement therapy is not fully elucidated but includes immunomodulatory effects.

The safety and efficacy of IVIg was evaluated in 6 prospective, open-label, single-arm, multicenter studies performed in Europe (ITP [16, 19], primary immunodeficiency [PID] [16], and chronic inflammatory demyelinating polyneuropathy [CIDP] [16, 22, 10] studies) and the United States of America (USA) (PID [16] study). The safety and efficacy profile of IVIg can be found in the respective European Medicines Agency (EMA) and Food and Drug Administration (FDA) prescribing information [16, 2].

